10.2.1 Overview of Treatment-Emergent Adverse Events

An AE overview summary table will be prepared including the number of subjects reporting an AE, the percentage of subjects (%) with an AE, and the number of events (E) reported, for the following categories:

- Treatment-emergent adverse events
- Deaths
- Serious adverse events
- Adverse events leading to withdrawal
- Severe and life threatening adverse events
- Adverse drug reactions

10.2.2 Incidence of Adverse Events

The number and percentage of patients experiencing a specific TEAE, as well as the number of events reported, will be tabulated by SOC, preferred term, and treatment group, overall and by age group. Additional summary tables will be provided for AEs by maximum intensity and by relationship to study treatment. Additional summaries for related AEs, serious AEs, AEs leading to withdrawal, and AEs leading to death will be generated. Non-serious AEs with an incidence of 5% or greater in any treatment group will also be summarized.

10.2.3 Data Listings

Supportive data listings will be provided for:

- All adverse events
- Serious adverse events
- Adverse events leading to death
- Adverse events leading to withdrawal

A mapping of adverse event verbatim terms to MedDRA preferred terms and system organ class will also be created.

10.3 Safety Laboratory Variables

Baseline for all laboratory analyses will be the values obtained at the last assessment prior to the first dose of study treatment. Treatment-emergent laboratory data will include tests completed after the first dose of study treatment through the residual time of drug effect. End of trial will include the last post-baseline observations during the trial.

10.3.1 Summary Statistics

At each nominal time point, the actual value and change from baseline (pre-treatment) will be summarized using the number of non-missing observations, mean, median, minimum, maximum and standard deviation for each treatment group, overall and by age group.

10.3.2 Laboratory Variable Changes Relative to Normal Range

Changes relative to normal ranges will be presented with shift tables showing the total number of subjects, and number and percentage of subjects who experienced a shift from baseline. The following categories for shift tables are defined:

- Low: Values which are below the lower reference range limit;
- Normal: Values which are within the lower and upper reference range;
- High: Values which are above the upper reference range limit.

For all haematology and clinical chemistry variables, shift tables will be prepared to compare baseline values to the worst post-treatment value.

10.3.3 Markedly Abnormal Changes

A summary table will be prepared that displays for each laboratory variable the number and percentage of subjects with normal baseline values who had at least one pre-specified markedly abnormal value anytime during the treatment period. The summary table will be presented by treatment group, overall and by age group. Pre-specified markedly abnormal criteria for laboratory tests are given in Appendix 1.

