#### 4.1.2 Exclusion Criteria

The presence of any of the following excludes a subject from study enrollment:

- 1. Acute surgical abdominal conditions (e.g., acute obstruction or perforation)
- 2. Hospitalized for inflammatory bowel disease
- 3. Any prior colorectal surgery, excluding appendectomy, hemorrhoid surgery, or prior endoscopic surgical procedures (subjects with diagnostic colonoscopy are not excluded)
- 4. Colon disease (history of colonic cancer, toxic megacolon, toxic colitis, idiopathic pseudo-obstruction, hypomotility syndrome, colon resection)
- 5. Ascites
- 6. Gastrointestinal disorder (active ulcer, outlet obstruction, retention, gastroparesis, ileus)
- 7. Upper gastrointestinal surgery (gastric resection, gastric banding, gastric bypass)
- 8. Significant cardiovascular disease as determined by the investigator
- 9. If subject has a history of renal insufficiency, serum creatinine and potassium must be within normal limits
- 10. Participation in an investigational study within 30 days prior to receiving study medication (or within 60 days for investigational drugs with an elimination half-life >15 days)
- 11. Any clinically significant laboratory value at screening, including pre-existing electrolyte abnormality, based on clinical history that the Investigator feels may affect the study evaluation

Trial Code: 000103 Date: 28-Jul-2014

E-Protocol Amendment-18395; Ver. 5 Supersedes: 4 Page 26 of 65

12. Hypersensitivity to active ingredients

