### 7.2.3 Clinical Laboratory Variables

All laboratory measurements will be performed using appropriately validated methods by the study site's local laboratory. All sites should follow their local regulations for sample handling and storage.

Laboratory values will be reported to the investigator and sponsor (or the sponsor's representative) and will be entered into the eCRF database, which will be maintained by a clinical research organization selected by the Sponsor.

Out-of-range values will be described in the reference ranges to be provided by the local laboratory. Investigators will assess all out of range values as being either clinically significant or not clinically significant via the eCRF.

Sites will be specially instructed to review all laboratory results in order to determine if the subject is eligible for study participation, and to determine any AEs post study drug administration.

Samples will be collected during Visits 1, 3 and 4 for determination of the following test values:

- Hematology panel:
  - o Full complete blood count and differential
- Coagulation panel:
  - o Prothrombin time, activated partial thromboplastin time
- Full chemistry panel:
  - o Calculated creatinine clearance
  - o Serum magnesium (Mg++)
  - o Serum chemistry: glucose, blood urea nitrogen, potassium, sodium, chloride, calcium, total protein, albumin, total bilirubin, alkaline phosphatase, aspartate aminotransferase, alanine aminotransferase, bicarbonate and gamma glutamyl transferase
- Urinalysis panel

In addition, urine pregnancy tests will be performed at the local laboratory for female subjects of childbearing potential at Visits 1 and 2.

Trial Code: 000103 Date: 28-Jul-2014

E-Protocol Amendment-18395; Ver. 5

Supersedes: 4 Page 37 of 65

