#### 8 ADVERSE EVENTS

#### **Adverse Event Definition** 8.1

An AE is any untoward medical occurrence in a subject participating in a clinical trial. It includes:

- Any unfavorable and unintended sign, symptom or disease temporally associated with the use of the IMP, whether or not considered to be caused by the IMP
- AEs commonly observed and AEs anticipated based on the pharmacological effect of the IMP
- Any laboratory abnormality, vital sign or finding from physical or gynecological examination assessed as clinically significant by the investigator (note: findings from assessments and examinations done during screening are not AEs, but are recorded as medical history.)
- Accidental injuries, reasons for any change in medication (drug and/or dose), reasons for any medical, nursing or pharmacy consultation, or reasons for admission to hospital or surgical procedures
- Overdoses and medication errors with and without clinical consequences

An adverse drug reaction (ADR) is an AE evaluated by the investigator as being probably or possibly causally related to treatment with the IMP.

A serious ADR is an SAE evaluated by the investigator and/or by Ferring as being probably or possibly causally related to treatment with the IMP (further described in Section 8.2.2).

An unexpected AE is an AE not identified in nature, severity, or frequency in the section "Undesirable Effects" in the sponsor's current Investigator's Brochure and current approved label.

A treatment-emergent AE is any AE that begins during the treatment period, or is a worsening of a pre-existing medical condition. The treatment period is the period during which a subject receives IMP.

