10.4.2 Markedly Abnormal Changes

Summary tables will be prepared displaying the number and percentage of subjects with normal baseline values who had one or more pre-specified markedly abnormal treatment-emergent values. Summaries will be provided by treatment group, overall and by age group. Pre-specified markedly abnormal criteria for vital signs are given in Appendix 1.

For orthostatic changes in blood pressure and pulse rate, the following criteria are suggestive of fluid volume depletion [1]:

- a decrease in systolic blood pressure greater than or equal to 20 mmHG within 3 minutes of standing,
- a decrease in diastolic blood pressure greater than or equal to 10 mmHG within 3 minutes of standing, or
- an increase in heart rate (pulse rate) greater than or equal to 30 beats per minute (bpm) in the presence of a drop in blood pressure (systolic, diastolic or both).

The number and percentage of subjects whose changes meet these pre-specified criteria will be summarized by treatment group, overall and by age group.

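### The markedly abnormal laboratory table (SAP 10.3.3) admits only children with normal baselines, so no laboratory count picks up a mildly abnormal baseline that worsens to an Appendix 1 marked abnormality

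*SAP*

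**What the plan says.** SAP 10.3.3 defines one table on the Appendix 1 laboratory limits: "the number and percentage of subjects with normal baseline values who had at least one pre-specified markedly abnormal value anytime during the treatment period". It does not say what a normal baseline is; I take it as within the reference range, the meaning used in 10.3.2.

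SAP 10.3.2 adds shift tables with three categories (Low, Normal, High) set by the reference range. For haematology and chemistry, "shift tables will be prepared to compare baseline values to the worst post-treatment value". The output is the total number of subjects and the number and percentage with a shift.

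SAP 10.4.2 puts the same condition on the vital-signs table: "subjects with normal baseline values who had one or more pre-specified markedly abnormal treatment-emergent values".

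The protocol allows children with out-of-range values to enter. Exclusion 11 (4.1.2) removes only this: "Any clinically significant laboratory value at screening, including pre-existing electrolyte abnormality, based on clinical history that the Investigator feels may affect the study evaluation".

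Protocol 7.2.3 fixes the safety samples: "Samples will be collected during Visits 1, 3 and 4 for determination of the following test values".

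**The concern.** The laboratory part of the secondary safety endpoint is the incidence of abnormal findings, with no condition on baseline (Protocol 2.2, SAP 2.2.2). Protocol 1.3 names children among those in whom bowel preparation can cause considerable dehydration. The table built to count marked laboratory abnormalities against fixed limits nevertheless leaves out every child whose baseline for that variable was out of range, whatever happens after dosing. With 15 children per arm, a single case matters to the description.

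The vital-signs table raises a second issue. Protocol 9.8.5 plans the incidence of markedly abnormal changes without a baseline condition. SAP 10.4.2 adds one, and SAP Section 12, which lists departures from the protocol analyses, does not mention it.

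**Working it through.** The plan states no figure for these tables, so there is none to reproduce. The check applies the rules to cases and then sizes the gap.

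**1. The rules applied to three cases.** Appendix 1 supplies the marked limits. The reference limits and patient values are assumed for illustration.

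| Variable | Baseline → after dosing | Assumed lower reference limit | Appendix 1 low limit | Marked? | Shift in 10.3.2? | Counted in 10.3.3? |
|---|---|---|---|---|---|---|
| Potassium, mmol/L | 3.4 → 2.9 | 3.5 | 3 | yes | no (Low to Low) | no |
| Haematocrit, % | 33 → 29 | 35 | 30 | yes | no (Low to Low) | no |
| Albumin, g/L | 32 → 24 | 35 | 25 | yes | no (Low to Low) | no |

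A move from High to markedly Low would count as a shift, so the gap is same-direction worsening. The shift tables for worst value cover haematology and chemistry only, so coagulation lacks even that output.

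**2. Chance that a case goes uncounted.** Let N = 45 Prepopik children (SAP 3.2), q = share with an out-of-range baseline for a variable, and a = share of those who worsen to a marked value. Neither q nor a is in the documents. Expected uncounted cases = N·q·a, and P(at least one) = 1 − (1 − q·a)^N. With q = 20% and a = 10%: 45 × 0.20 × 0.10 = 0.9 cases, and 1 − 0.98^45 = 0.60.

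| q | a = 5% | a = 10% | a = 20% |
|---|---|---|---|
| 10% | 0.20 | 0.36 | 0.60 |
| 20% | 0.36 | 0.60 | 0.84 |
| 30% | 0.49 | 0.75 | 0.94 |
| 40% | 0.60 | 0.84 | 0.98 |

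**3. Number against percentage.** Let b = 5% be the marked rate with a normal baseline (assumption), with q = 20% and nobody markedly abnormal at baseline. The table counts 45 × 0.80 × 0.05 = 1.8 cases.

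- a = 10%: all cases = 1.8 + 0.9 = 2.7, so 0.9/2.7 = 33% are uncounted. The percentage is 1.8/36 = 5.0% in the restricted table and 2.7/45 = 6.0% in all children.
- a = 5%: 1.8/36 = 5.0% and 2.25/45 = 5.0%, so no change.
- a = 0: 1.8/36 = 5.0% and 1.8/45 = 4.0%, so the restricted figure is the higher one.

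If the whole group stays in the denominator, the restricted figure at a = 10% is 1.8/45 = 4.0% against 6.0%, which is too low. Section 10.3.3 does not state the denominator.

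**4. Precision.** With zero events in m children, the exact two-sided 95% upper limit is 1 − 0.025^(1/m). At q = 20%, m falls from 45 to 36 and the limit rises from 7.9% to 9.7%. In one arm, m falls from 15 to 12 and the limit rises from 21.8% to 26.5%.

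**5. The time window.** Section 10.3.3 uses the treatment period, without defining it for laboratory data. The opening of 10.3 says "Treatment-emergent laboratory data will include tests completed after the first dose of study treatment through the residual time of drug effect", with no length given. Section 10.3.2 takes the worst value after treatment. These are three different descriptions. All safety samples after dosing come from Visit 3 (before colonoscopy) and Visit 4 (5 ± 2 days, so Days 3 to 7).

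**The case against.** Restricting the table to normal baselines is a stated choice that isolates new abnormalities, the objective is descriptive, and Protocol 9.8.3 does not call for this laboratory table at all. Exclusion 11 names electrolyte abnormality, and exclusion 9 requires normal potassium and creatinine where there is a history of renal insufficiency. Both narrow the affected group without emptying it. All of this stands, and it limits the weight of the point.

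Three stronger readings are tempting, and the documents do not support them.

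- *The child is counted nowhere.* A reader might infer this, but the child is in the shift-table total and in the minimum, maximum and change summaries (SAP 10.3.1), and the values are listed (10.3.4). Investigators must classify every out-of-range value (Protocol 7.2.3), and one judged clinically significant is an adverse event (Protocol 8.1), tabulated without a baseline condition (SAP 10.2.2). For fluid loss, the orthostatic count in 10.4.2 has no stated baseline restriction. What these outputs do not give is an incidence against the fixed laboratory limits, and the adverse-event route rests on individual judgement.
- *No sample falls in the window, so the table must show zero.* This takes "The treatment period is the period during which a subject receives IMP" from the protocol's adverse-event section. The opening of SAP 10.3 starts the laboratory window at first dose, and a Visit 3 sample fits it. SAP 7.3, for medications, uses the same term for a span from first administration to the last visit (which it numbers 6, though the schedule ends at Visit 5). The wording needs clarifying; a zero count does not follow.
- *Incidence is understated.* This holds for the number of cases. The percentage can rise, fall or stay the same, as step 3 shows.

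Nor do the documents show that a mildly out-of-range value marks a child with less physiological reserve.

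**Conclusion.** The point holds in a limited form. A child whose mildly abnormal baseline worsens in the same direction to an Appendix 1 marked abnormality is missed by every laboratory count based on those limits. The number of such abnormalities can be understated. If the whole arm is the denominator, one missed child is 1/15 = 6.7 percentage points; the direction of any change in the percentage is otherwise unknown. The probabilities of 0.20 to 0.98 rest wholly on assumed rates and show only that a missed case is plausible at this sample size.

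The vital-signs table has the same restriction, added without being listed in SAP Section 12. One caution applies there: Appendix 1 gives only marked limits for pulse and blood pressure, so a normal baseline is undefined. If it means not markedly abnormal, that table already does what is asked below.

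Neither the primary analysis nor the sample-size statement is affected. This is a cheap improvement to the safety description.

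**What to change.** In SAP 10.3.3 and 10.4.2:

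- Count all subjects not already markedly abnormal at baseline who have a markedly abnormal value at any assessment after first dose, and state the matching denominator.
- Split the count by baseline status (normal; abnormal but not marked), and keep the normal-baseline count as its own column. Define a normal baseline, for vital signs in particular.
- Use one window, from first dose and covering Visits 3 and 4, in 10.3, 10.3.2 and 10.3.3. Show the two visits separately: Protocol 1.3 reports that shifts in the adult studies resolved within 24 to 48 hours after the procedure, so a Day 3 to 7 sample answers a different question from the Visit 3 sample.
- List in SAP Section 12 any baseline condition kept on the vital-signs table.

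The cost is a wording change, one extra column and a possibly less favourable reported figure. No new data are needed.

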10.3.4 Data Listings

All clinical laboratory values outside normal range will be listed separately by subject number, including demographic information and abnormal flag values.

10.4 Vital Signs

Baseline for all vital signs analyses will be the values obtained at the last assessment prior to the first dose of study treatment. Treatment-emergent vital signs data will include tests completed after the first dose of study treatment through the time of residual drug effect. End of trial will include the last post-baseline observation during the trial.

10.4.1 Summary Statistics

At each nominal time point, the actual value and change from baseline (pre-treatment) will be summarized using the number of non-missing observations, mean, median, minimum, maximum and standard deviation for each treatment group, overall and by age group. In this study, blood pressure and pulse are first measured after at least 5 minutes resting in supine position and after 3 minutes in standing position. Summaries will be provided for vital signs recorded in the supine and standing positions, as well as the change from supine to standing (orthostatic measurement).

10.4.2 Markedly Abnormal Changes

Summary tables will be prepared displaying the number and percentage of subjects with normal baseline values who had one or more pre-specified markedly abnormal treatment-emergent values. Summaries will be provided by treatment group, overall and by age group. Pre-specified markedly abnormal criteria for vital signs are given in Appendix 1.

For orthostatic changes in blood pressure and pulse rate, the following criteria are suggestive of fluid volume depletion [1]:

- a decrease in systolic blood pressure greater than or equal to 20 mmHG within 3 minutes of standing,
- a decrease in diastolic blood pressure greater than or equal to 10 mmHG within 3 minutes of standing, or
- an increase in heart rate (pulse rate) greater than or equal to 30 beats per minute (bpm) in the presence of a drop in blood pressure (systolic, diastolic or both).

The number and percentage of subjects whose changes meet these pre-specified criteria will be summarized by treatment group, overall and by age group.

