### 7.2.2 Vital Signs

Orthostatic vital signs (supine and standing blood pressure and pulse) will be measured at Visits 1 through 4.

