7.1.2 Vital Signs at Baseline

Baseline vital signs include systolic and diastolic blood pressure and pulse in the supine and standing positions. The change from supine to standing in systolic and diastolic blood pressures will also be presented as a measure of orthostatic change.

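### The SAP's orthostatic count does not separate children who already met the criteria before dosing from new cases

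*SAP*

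**What the plan says.** SAP 10.4.2 contains two counts.

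- **Appendix 1 limits.** This count covers children whose baseline was normal and who had a markedly abnormal value arising on treatment.
- **Orthostatic criteria.** One is "a decrease in systolic blood pressure greater than or equal to 20 mmHG within 3 minutes of standing". The others are a diastolic fall of at least 10 mmHg on standing, and a pulse rise of at least 30 bpm accompanied by a fall in pressure. The rule for the count is: "The number and percentage of subjects whose changes meet these pre-specified criteria will be summarized by treatment group, overall and by age group".

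The readings that could serve as a pre-dose reference are scheduled. Protocol 7.2.2 says: "Orthostatic vital signs (supine and standing blood pressure and pulse) will be measured at Visits 1 through 4". Visits 1 and 2 precede dosing, because medication is only dispensed at Visit 2 (Protocol 6.2). SAP 10.4 also defines the reference: "Baseline for all vital signs analyses will be the values obtained at the last assessment prior to the first dose of study treatment". It defines treatment-emergent vital signs as those taken after the first dose.

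Three other places bear on the point. SAP 7.1.2 says of baseline: "The change from supine to standing in systolic and diastolic blood pressures will also be presented as a measure of orthostatic change". SAP 10.4.1 plans descriptive statistics at each time point, with change from baseline, and includes the supine-to-standing change. SAP 10.4.3 flags abnormal orthostatic measures in listings at every time point. SAP 12 names the orthostatic summaries as an addition to the protocol's analyses, so the protocol supplies no missing rule.

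**The concern.** The changes being counted are differences between two postures at one visit. They contain no contrast between before and after dosing. A child with a habitual postural drop shows it at Visit 2 and again at Visit 3, and the second reading enters a percentage labelled as suggesting volume depletion.

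Protocol Table 1-1 lists hypovolemia among three risks, and the safety objective is to describe safety in this age range. The percentage within each arm is therefore itself a result. Randomisation balances pre-existing positives between arms in expectation, but it does not remove them from the within-arm figure. With about 15 children per arm, one such child moves that figure by 1/15 = 6.7 percentage points.

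**Working it through.** **Text comparison.** The plan states no figure for this count, so there is none to reproduce.

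| Planned output | Normal baseline required? | Limited to post-dose? | Shows which positives are new? |
|---|---|---|---|
| 10.4.2, Appendix 1 limits | yes | yes | yes, by restriction |
| 10.3.3, laboratory limits | yes | treatment period | yes, by restriction |
| 10.4.2, orthostatic criteria | not stated | not stated | no |
| 7.1.2 and 10.4.1 | not applicable | by time point | no, group statistics |
| 10.4.3 | not applicable | every time point | only by reading listings |

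**Size.** The quantity that matters is the number of children positive both before and after dosing:

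n × q × s,

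where n = 15 (SAP 3.2), q is the rate of meeting any criterion at one reading, and s is the share of post-dose positives who were also positive before dosing. The documents give neither q nor s. I simulated normally distributed postural changes at two visits with no depletion and applied the three criteria. For the third I required a pulse rise of at least 30 bpm with any fall in systolic or diastolic pressure.

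Assumptions: mean systolic change 0; mean diastolic change 0 to +4 mmHg; within-child correlation between visits 0.3 to 0.6; systolic, diastolic and pulse changes independent of each other.

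| SD systolic / diastolic (mmHg); pulse rise mean / SD (bpm) | Mean diastolic change (mmHg) | Correlation | q | s | 15 × q × s |
|---|---|---|---|---|---|
| 8 / 6; 12 / 8 | +4 | 0.3 | 2.3% | 6.4% | 0.02 |
| 8 / 6; 12 / 8 | +3 | 0.3 | 2.9% | 7.7% | 0.03 |
| 8 / 6; 12 / 8 | 0 | 0.6 | 6.2% | 29.2% | 0.27 |
| 9 / 7; 15 / 10 | +3 | 0.3 | 8.6% | 16.0% | 0.21 |
| 9 / 7; 15 / 10 | 0 | 0.6 | 13.3% | 37.2% | 0.74 |
| 10 / 8; 18 / 12 | 0 | 0.3 | 22.5% | 32.1% | 1.08 |
| 10 / 8; 18 / 12 | 0 | 0.6 | 22.5% | 45.8% | 1.55 |

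Lowest: 15 × 0.023 × 0.064 = 0.02. Highest: 15 × 0.225 × 0.458 = 1.55. Setting the systolic-diastolic correlation to 0.5 lowers the highest value to 1.40. The lower end depends heavily on the assumed mean diastolic change: in the first scenario q is 6.2% at zero and 2.9% at +3 mmHg.

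**What the split does not remove.** In these runs 1 − s, from 1 − 0.458 = 54% to 1 − 0.064 = 94%, of the post-dose positives were negative before dosing. They arise by chance and would still appear as new cases.

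**Effect on a reported percentage.** With pre-dose rate q, true new-onset rate e and persistence r, a post-dose count without a reference reports q × r + (1 − q) × e. Taking q = 10%, e = 10% and r = 0.5, all assumed, gives 0.05 + 0.09 = 14%, against 10% among children negative before dosing.

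**The case against.** The best defence is that the orthostatic sentence sits under SAP 10.4, which defines both baseline and treatment-emergent data for vital signs. A post-dose reading of the count is natural, and the table shells, held in a separate document, may already impose it. This part stands. A reader might infer that a child positive only before dosing is counted. The documents do not establish that, because the visit window is not stated. A post-dose window would still count a child who is positive at both times.

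SAP 10.4.1 also covers more than 7.1.2 does. It names blood pressure and pulse before turning to the supine-to-standing change, so postural pulse is plausibly summarised at each time point, including before dosing. That too stands, but a mean and SD cannot show which children were already positive.

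The SAP does not call the count a preparation effect. Adverse events and laboratory shifts also bear on hypovolemia, and the randomised reference group carries the same expected share of pre-existing positives. These points limit the consequence. Because the reference children also take a preparation, their rate is not a rate without one; the pre-dose readings give that.

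It would also be wrong to treat every background positive as affected. At the q values above that is 15 × 0.023 = 0.3 to 15 × 0.225 = 3.4 children per arm, most of whom the split would not reclassify.

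**Conclusion.** The point holds in limited form and is minor. As written, SAP 10.4.2 counts a child who met the orthostatic criteria before dosing and still meets them afterwards, and no planned table separates that child from a new case. The likely size is about 0.02 to 1.6 children per arm of 15. That range rests wholly on assumed postural SDs, means and within-child correlation, since the documents give no background rate. The consequence is confined to a descriptive safety percentage; the primary endpoint, sample size and conduct are unaffected.

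One limit applies to any repair. In Protocol 6.3 the Visit 3 reading explicitly called orthostatic is listed after colonoscopy, while the pre-procedure list mentions only vital signs. A post-procedure reading also reflects sedation and the procedure, so even a new case at Visit 3 cannot be put down to the preparation alone.

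**What to change.** In SAP 10.4.2:

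1. State that the orthostatic count uses readings after the first dose, reported by visit.
2. For each post-dose visit, show a two-by-two table (criteria met at the last pre-dose reading, yes or no, by met after dosing, yes or no) by treatment group and age group. Keep all four cells, so that new cases and pre-dose positives are both visible. The cell positive only before dosing gives a rough gauge of chance reversals, which helps in reading the new cases.
3. Label the Visit 3 reading by whether it was taken before or after colonoscopy, and do not pool the two.

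Adding the postural pulse change to SAP 7.1.2 is optional, because 10.4.1 largely covers it.

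The cost is a few lines of SAP text and one small table. No new measurement is needed, but the team should confirm that the database identifies the timing of the Visit 3 reading.
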